- No local anesthesia will be administered as it would alter the pain perception of the patient unless necessary.

Evaluations

1. Clinical evaluation

- The clinical assessment will be at 3-, 6- and 12-month intervals to evaluate
 - a) Postoperative pain
 - b) Any signs or symptoms of pulpitis
 - c) Vertical and horizontal percussion tests
 - d) Tooth-color alterations and fistulas presence.
 - e) Restoration success will be evaluated according to the criteria of atraumatic restorative treatment by Phantumvanit et al. (1996) (45). It is based on the retention of the material in the cavity and the presence of secondary caries.
 - f) Restorations which will receive a score of 0, 1 or 7 will be considered successful while those having a score of 2, 3, 4 or 8 will be considered failures. Those which will receive a score of 5, 6 will be excluded from the analysis (Appendix IV).

2. Radiographic evaluation

- Periapical radiograph will be taken immediately after clinical procedure and at 6- and 12-months intervals during follow up period to confirm the clinical evaluation.⁽⁴⁶⁾
- It will be obtained by the long cone paralleling technique to minimize the distortion using the film holders.⁽⁴⁷⁾
- The radiographic evaluation will be performed using the radiographic subtraction method and the assessment of the density of the remaining dentin by gray-scale analysis using the Image j 1.37 V program⁽³¹⁾.
- Therefore, a greater degree of density on the image will indicate a greater success.

- Any case that will exhibit pulp involvement associated with a radiolucent image or any signs for periapical lesions will be considered unsuccessful treatments.

3. Evaluation of time required to perform procedure

- The time needed for complete caries removal will be recorded for each caries removal method.
- The timing of each procedure will set immediately upon the first application by using a stopwatch and turned off when there is no carious dentin left in the cavity.
- After complete removal of decay, the teeth will be restored with glass ionomer filling as a temporary restoration to be replaced after the follow up period using Composite filling sandwich technique.

4. The participants' pain assessment:

- Subjective pain will be assessed after caries removal by means of Wong-Baker faces scale⁽⁴⁸⁾. It consists of faces with different facial expression for happiness and pain and is scored from 0-5 as 0 is very happy and feels no pain and 5 is very painful (APPENDIX III).

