- 1- Clinical effectiveness of each material during the follow up period at 3-, 6- and 12-months intervals confirmed with radiographic findings at 6- and 12-month intervals.
- 2- Timing required for complete caries removal following each caries removal method
- 3- Participants' subjective pain reaction following each caries removal method.
- 4- Antimicrobial effect of both CMCR agents by comparing the colony forming units (CFU) at the treatment visit before and after application of each agent compared to conventional caries removal method.

Follow up

All patients will be recalled after 3-, 6- and 12-month intervals. On the day of the recall appointment, patient preparation will be done as mentioned before.

Outcome assessment

- 1- Restorations which will receive a score of 0, 1 or 7 will be considered successful while those having a score of 2, 3, 4 or 8 will be considered failures.
- 2- Any clinical sign and symptoms teeth with pain, intraoral or extra oral abscess formation and fistula formation will be recorded as unsuccessful treatments
- 3- Any periapical lesions on radiography during follow-up will be recorded as unsuccessful treatments.

Study Plan

[figure not shown]

Figure 1: Flow chart of the study plan

STATISTICAL ANALYSIS

The statistical Package for Social Sciences (SPSS)* version 27.0 for Windows will be used for data analysis.

All data will be collected; The Chi square test will be used to compare the difference between the three groups regarding the clinical success, the T-test or the Mann-Whitney U test will be used to analyze the differences between the microbiological samples. The data will be graphically presented with suitable graphs. The level of statistical significance will be set at 5%.

* SPSS Inc., Chicago, IL, USA

ETHICAL CONSIDERATIONS

1. The research protocol will be approved by the Research Ethics Committee of Alexandria University Faculty of Dentistry (IRB No. 001056 –IORG 0008839) prior to any research-related activities.
2. All research activities involving human subjects will abide by the Declaration of Helsinki⁽⁵³⁾ and other ethical guidelines adopted by the Research Ethics Committee of Alexandria University Faculty of Dentistry.
3. Benefits:
 - It will provide caries treatment for young permanent molars in children using minimally invasive atraumatic procedures.
 - It will allow overcoming the disadvantages of conventional treatment with local anesthesia

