APPENDIX IV

Table (2): Evaluation scores criteria of atraumatic restorative treatment proposed by Phantumvanit.⁽⁴⁵⁾

Codes	Description
0	Present, in good condition
1	Present, slight marginal defect, no repair needed
2	Present, marginal defects 0.5-1.0 mm, repair needed
3	Present, marginal defects > 1.0 mm, repair needed
4	Not present, restoration partially or completely missing
5	Not present, restoration replaced by other restoration
6	Tooth missing, exfoliated or extracted
7	Present, slight wear, no repair needed
8	Present, wear > 0.5 mm, repair needed

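### Excluding replaced restorations and lost teeth (codes 5 and 6) from the success analysis can remove real failures from the 12-month comparison

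*Combined protocol and SAP*

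**What the plan says.** Under Evaluations, 1. Clinical evaluation, item f, scores 0, 1 and 7 are successes and scores 2, 3, 4 and 8 are failures. For the two remaining scores the rule is: "Those which will receive a score of 5, 6 will be excluded from the analysis (Appendix IV").

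Appendix IV, Table (2) defines the codes that matter here:
- Code 5: "Not present, restoration replaced by other restoration".
- Code 6: "Tooth missing, exfoliated or extracted".
- Code 4, which counts as a failure: "Not present, restoration partially or completely missing".
- Code 3, also a failure: "Present, marginal defects > 1.0 mm, repair needed".

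The section on procedure time describes the restoration as a "glass ionomer filling as a temporary restoration to be replaced after the follow up period". Study outcome, item 1 compares "Clinical effectiveness of each material during the follow up period at 3-, 6- and 12-months intervals".

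Other rules also define failure. The radiographic evaluation section states: "Any case that will exhibit pulp involvement associated with a radiolucent image or any signs for periapical lesions will be considered unsuccessful treatments". Outcome assessment, items 2 and 3 classify teeth with pain, abscess, fistula or periapical lesions as unsuccessful. Outcome assessment, item 1 repeats the success and failure scores but does not mention 5 or 6. The Statistical analysis section names a chi-square test across the three groups for clinical success. It defines no analysis set and no rule for missing outcomes.

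**The concern.** Codes 5 and 6 are assigned after randomisation and can be consequences of the treatment under test. The only replacement the protocol plans comes after follow-up, so a code 5 within 12 months is an unplanned replacement. Natural exfoliation is not expected for a first permanent molar at 8-10 years, so a code 6 most plausibly means an extraction or another loss. A missing restoration is a failure under code 4, yet the same restoration lost and then replaced is no longer counted.

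The rule can also undo a failure already on record. A restoration scored 2, 3, 4 or 8 at 3 or 6 months is a failure at that visit. If it is then replaced, it is code 5 at 12 months and leaves that comparison. Twelve months is the time point of the one-year rates behind the sample size.

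Where such cases are failures, the reported 12-month success rate is too high in any arm where they occur, and who is analysed depends on the outcome. This bears on the primary aim.

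**Working it through.** **Inputs.** From Sample size estimation: alpha 5%, power 80%, one-year success 95% (chemo-mechanical) and 67% (comparator), 30 per group, raised to 36 for loss to follow-up. Sidedness is not stated; two-sided is assumed because it reproduces the 30. The share s of an arm's failures that end up coded 5 or 6 is not in the documents and is an assumption throughout.

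**Step 1: the plan's own figure.** Two-sided, pooled variance, no continuity correction, mean proportion 0.81:

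n = [1.96·√(2·0.81·0.19) + 0.8416·√(0.95·0.05 + 0.67·0.33)]² / 0.28² = (1.0874 + 0.4362)² / 0.0784 = 29.6, so 30 per group.

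Power at 30: Φ[(0.28·√30 − 1.0874)/0.5183] = Φ(0.861) = 80.5%. The stated 30 is reproduced. The three-group Pearson chi-square (2 df), by exact enumeration with two arms at 95% and one at 67%, has 88.9% power at 30 per arm.

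**Step 2: effect of the exclusion.** Of n teeth, np succeed and n(1−p) fail. If s·n(1−p) failures are dropped, the analysed success rate is

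p* = p / [1 − (1−p)s].

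**Step 3: s = 10% in every arm, on the assumption that the planned rates count such cases as failures.**
- Gel: 0.95/0.995 = 95.5%, with 0.15 of 30 teeth dropped.
- Hand excavation (ART): 0.67/0.967 = 69.3%, with 1.0 of 30 teeth dropped.
- The difference falls from 28.0 to 26.2 points.
- Two-arm power is 77.3% with n held at 30, or 76.6% with n reduced by the dropped teeth.
- Three-group power is 86.4% at 30 per arm.

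**Step 4: larger shares, the same in every arm (assumptions only).**

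| s | Gel | ART | Difference (points) | Two-arm power, n = 30 | Two-arm power, n reduced | Three-group power, 30 per arm | Three-group power, 36 per arm |
|---|---|---|---|---|---|---|---|
| 10% | 95.5% | 69.3% | 26.2 | 77% | 77% | 86% | 93% |
| 25% | 96.2% | 73.0% | 23.2 | 71% | 69% | 81% | 89% |
| 50% | 97.4% | 80.2% | 17.2 | 56% | 54% | 66% | 76% |

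The last column supposes that all 36 per arm are analysed, with no other loss.

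**Step 5: unequal shares.** With s = 10% in ART only, the difference is 95.0 − 69.3 = 25.7 points. In the gel arms only, it is 95.5 − 67.0 = 28.5 points. At s = 25% the two figures are 22.0 and 29.2. If two arms both truly had 67% success and s were 20% in one of them, the analysis would show 0.67/0.934 = 71.7% against 67%, a false difference of 4.7 points. The bias has no fixed direction.

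**Step 6: do other rules rescue these teeth?** Outcome assessment items 2-3 and the radiographic rule would class some of them as unsuccessful, but no sentence says those rules override item f. A tooth replaced or extracted between recalls, with no earlier recorded sign, meets none of them.

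**The case against.** The strongest reply is that the effect may be small and partly covered already. Children with pain, pulpal infection or pulp exposure are excluded, so extractions may be few. Three of the four failing codes (2, 3 and 8) call for repair, and a repaired restoration need not become code 5. No text plans replacement during follow-up, so the 25% and 50% rows have no support in the documents. The planned three-group test stays above 80% power at the 10% and 25% shares even with 30 per arm. One can also argue that a failure once recorded is naturally read as permanent, since item f and Outcome assessment item 1 both say such teeth are to be considered failures. All of this limits the size. It does not remove the gap: the exclusion is explicit, the carry-forward is not, and neither is any order of precedence.

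A reader might infer that one excluded tooth could overturn the result. With gels at 28/30 and 29/30, the Pearson p-value moves from 0.031 (ART 23/30) to 0.065 (ART 23/29). The expected failure counts are only about 3 per arm, however, and the exact (Fisher-Freeman-Halton) test gives 0.070 and 0.090, with no change of conclusion. That example should not carry weight.

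A reader might also infer that 30 per group is too few, on the view that the 95% and 67% already leave codes 5 and 6 out. The documents do not say how those rates were counted, so this is a query and not evidence of an error.

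Counting every code 5 or 6 as a failure is one defensible choice. Leaving out documented unrelated losses, such as trauma, is another, and the sensitivity analysis below covers it.

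**Conclusion.** The concern holds as a defect in the endpoint rule. Applied as written, item f can take real failures out of the 12-month comparison, including failures recorded at 3 or 6 months, and nothing in the plan prevents this. Confidence is high on the reading of the text and low on the size, because no rate for codes 5 and 6 is given. At an assumed 10% of failures dropped in every arm, the cost is about 2 points of difference and about 3 points of power. Larger shares would cost more, and unequal shares could bias the comparison in either direction. The documents do not support a claim that the result will be biased towards one method, or that the sample size is wrong. The point should be fixed before analysis.

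How secondary caries is scored is a separate clarification. Item e makes it part of restoration success, but no Appendix IV code and no item in the Outcome assessment list records it.

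**What to change.** In Clinical evaluation item f and in Outcome assessment:
1. For the primary analysis, count any code 5 or 6 recorded up to 12 months as a failure.
2. State that a failure recorded at an earlier visit, under Outcome assessment items 2-3 or under the radiographic rule, stays a failure whatever code the tooth later receives.
3. Record the reason for each replacement or tooth loss, and report these by arm.
4. As sensitivity analyses, show (i) the exclusion as now written and (ii) an analysis leaving out only losses with a documented unrelated cause such as trauma, from a short list fixed in advance.

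This changes how outcomes are counted, not how any tooth is managed. The cost is wording in two places, one recorded field and two tables, with no extra visit or radiograph. The downsides are that success rates may read slightly lower, a few unrelated losses will count as failures, and the recorded reason still comes from an examiner who is not blinded.

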Background: Minimally invasive dentistry continues to gain importance, especially in the treatment of permanent teeth with deep caries lesions and immature roots. Chemo-mechanical caries removal (CMCR) is an alternative to the conventional method and consists of the application of a proteolytic substance that softens carious dentin tissue and facilitates its removal using manual instruments. This method can be employed without the use of local anesthesia or burs, thereby preserving sound dental tissue.

Objective: To assess the clinical performance of Brix 3000 and Papacarie duo gel as chemo-mechanical caries removal agents (CMCR), their performance in terms of time required for the caries removal, patient subjective pain reaction, their radiographic success and their antimicrobial effect in comparison with Atraumatic Restorative Treatment (ART) hand excavation method for caries removal.

Methods: 100 children with age ranging between 8 and 10 years old who have at least one carious first permanent molar will be randomly divided into three groups. A three-arm randomized clinical trial where test groups, group I, caries removal will be using Brix 3000, and group II Papacarie duo will be used, while the control group hand excavation will be the method of caries removal. Dentin samples of three groups will be taken prior to and following caries removal. The total viable streptococci and lactobacilli count will be determined and expressed as colony forming units per milliliter (CFU). The time required for caries removal with each method will be calculated and the subjective pain reaction following each method will be recorded. After complete caries removal step, it will be followed by restoration with glass ionomer restoration. Patients will be followed up at 3-, 6- and 12-month intervals to determine the clinical success and at 6- and 12- month intervals for the radiographic success rate for each caries removal method.

Results: The data collected will be statistically evaluated with the suitable tests and tabulated.

Keywords: Minimally invasive, Young Permanent, Chemo-mechanical caries removal agents, Brix 3000.

INTRODUCTION

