Heading out of the contradictory results, no publication has reported the in vivo comparison between Papacarie duo and the newly developed CMCR agent Brix 3000 gel in terms of their clinical and radiographic success and their antimicrobial effect compared to the Art approach for caries removal in young immature permanent teeth. The null hypothesis of this study is that no statistically significant difference will be detected between both materials and ART approach regarding to their clinical performance, and their antimicrobial effect in young permanent molars during the follow up period.

AIM OF THE STUDY

Primary aim

- To assess and compare the effectiveness of two chemo-mechanical agents Brix 3000 and Papacarie duo in terms of their clinical and radiographic success in young permanent molars, in comparison with ART approach.

Secondary aims

- Determine the required time for complete caries removal for each method.
- Evaluation of patients' subjective pain reactions following each method.
- Evaluation of antimicrobial effect of two chemo-mechanical caries removal agents by comparing the colony forming units (CFU) at the treatment visit before and after the application of each agent compared to hand excavation method.

MATERIALS AND METHODS

Study design

This will be a randomized, parallel, three-arms controlled clinical trial, with a 1:1:1 allocation ratio. It will be set up and reported according to the CONSORT guidelines.⁽³⁰⁾

The PICOT question is:

Will children (8-10 years old) with class I carious lesion in the first permanent first molar (with ICDAS score 5 or 6) (population; P) using Brix 3000 or Papacarie duo gel (intervention; I) for Chemo-mechanical caries removal in comparison with ART approach (Hand excavation) (Control; C) show a greater success (outcome; O) at different time intervals over twelve months period (time; T)?

Study setting and location

The study will take place in the Department of Pediatric Dentistry and Dental Public Health at the Faculty of Dentistry and the Department of Microbiology and Immunology at the Faculty of Pharmacy, Alexandria University, Alexandria, Egypt.

Sample

Sample size estimation

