- Periapical x-ray radiographs will be taken for each tooth before enrolling it into the trial to determine that the carious lesion depth does not involve the pulp.

Intervention

- All the lesions in the children's oral cavity indicated for treatment will be treated and sampled for microbiological analysis prior to and following caries removal.
- On the day of the intervention, the children will be asked to refrain from tooth brushing in the morning, as well as eating and drinking (except water) for at least two hours before the appointment. ⁽⁴¹⁾

- The patients will be instructed to rinse with a cup of water, then the outer surface of the carious lesion will be washed with a flurry of water to avoid contamination of plaque bacteria. ⁽⁴²⁾
- The tooth will then be partially isolated using cotton rolls and saliva ejector.
- Two portions of dentin will be collected with sterile excavators from the middle of the cavity to perform the microbiological analysis of each tooth before and then after caries removal procedure. ⁽⁴¹⁾
- The dentin sample will then be inserted in a sterile test tube containing 1 mL of saline and transported to the microbiology laboratory within 1-2 hours. ⁽⁴³⁾
- Dentin sample weight will be calculated by measuring the difference between the weight of the whole set (sterilized bottle and transporting medium) and the previously determined weight of the set without dentin. ⁽⁴⁴⁾
- The bacterial count obtained for a given amount of dentin will be used to estimate the number of colonies present in 1 mg dentin (CFU/mg). ⁽⁴⁴⁾
- **In the CMCR group:** either Papacarie duo or Brix 3000 gel will be applied on the carious lesion of tooth and left undisturbed for 30-60 seconds, following manufacturer instructions ⁽²⁸⁾. This produces softening of carious dentin, which will be removed with a hand excavator. This step will be repeated 2-3 times until dentin demonstrates slight resistance with no tug-back sensation when tested with an exploratory probe while pressing an explorer into dentin, then the application of the chemo-mechanical agents will be stopped.
- The visual test for assessment of complete caries excavation will be based on non-turbid appearance of the CMCR agent used.
- **In the ART group** hand excavation will be performed to remove the carious tissue from the cavity by using a sterile sharp hand excavator. The cavity will be determined to be caries-free according to visual and tactile clinical criteria.

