- Each child will be trained to use the scale by first modeling and then asking each participant to think of the last time she/he felt something painful' and to select the facial expression that best represented his/her experience of discomfort.

5. Microbiological evaluation Procedure

- Samples from the carious lesion will be collected prior to and following complete caries removal for detection of the change in bacterial count (Streptococci and Lactobacilli counts).

a. Sample dilution

All samples will be dispersed by vortexing for 30 seconds then 10-fold serially diluted using sterile saline. A measure of the dilution will then be used for traditional plate culturing methods. ⁽⁴⁹⁾

b. Culture

Aliquots of 10 ml of each dilution will be inoculated into freshly prepared Rogosa agar media using a micropipette.

- Mitis Salivarius agar plates will be incubated anaerobically in an atmosphere containing 10% CO₂ at 37°C for 72 hours to detect Streptococcus mutans count
- Rogosa agar plates will be incubated aerobically at 37° C for 48 hours to detect Lactobacilli count.

c. Isolation and Enumeration

Following the predetermined incubation period, colonies grown on the specified media will be counted and represented as (CFU/ml). Streptococcus mutans will be identified based on their characteristic morphology on Mitis Salivarius agar plates. Similarly, Lactobacilli will be identified biochemically and microscopically on the basis of their morphology.

Colony count

The number of colonies will be determined and expressed as colony forming units using the following equation. ⁽⁵⁰⁾

$$\text{CFU/ml} = \frac{\text{n}^\circ \text{ of colonies} \times \text{dilution factor}}{\text{Volume taken in ml}^{(51)}}$$

6. Oral Health quality of life questionnaire

- Oral health quality of life will be assessed at one week recall appointment by using the Arabic validated version of the child perceptions questionnaire. ⁽⁵²⁾
- It consists of 25 items distributed among 4 domains: oral symptoms, functional limitations, emotional well-being, and social well-being. It is self-reported by children using a 5-point Likert scale (APPENDIX V), and responses range from 0–4 for each item. Hence, total scores range from 0 to 100, and higher scores indicate poorer OHRQoL. (APPENDIX VI)

STUDY OUTCOME

Treatment effect will be evaluated after the follow up period by comparing:

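### The microbiology analysis names a t-test or Mann-Whitney test without a contrast; paired before/after counts in three arms call for a baseline-adjusted comparison of each gel with hand excavation, with multiplicity control

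*Combined protocol and SAP*

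**What the plan says.** The design section states: "This will be a randomized, parallel, three-arms controlled clinical trial, with a 1:1:1 allocation ratio". Item 4 of Study Outcome describes the antimicrobial effect as "comparing the colony forming units (CFU) at the treatment visit before and after application of each agent compared to conventional caries removal method", and the last secondary aim says much the same. Under Intervention, dentin is taken from the cavity "to perform the microbiological analysis of each tooth before and then after caries removal procedure", so the two counts are paired within a tooth. Streptococci and lactobacilli are counted separately.

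The whole analysis plan for these data is that "the T-test or the Mann-Whitney U test will be used to analyze the differences between the microbiological samples", at a 5% significance level. The text does not say whether the t-test is paired, whether the comparison is before against after or arm against arm, whether counts are logged, how to choose between the tests, or whether several contrasts are adjusted for. The chi-square test for clinical success, in the same sentence, is expressly a comparison of the three groups.

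On the unit, Intervention has each dentin sample weighed and says the count "will be used to estimate the number of colonies present in 1 mg dentin (CFU/mg"). The abstract has "The total viable streptococci and lactobacilli count will be determined and expressed as colony forming units per milliliter (CFU"), and the enumeration step has "colonies grown on the specified media will be counted and represented as (CFU/ml"). The statistical section names no unit.

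**The concern.** The aim calls for a between-arm comparison that uses the before value, made for two gel-versus-ART contrasts and two organisms. The one clause provided can be read in at least two ways:

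- **Two-sample tests on change, each gel against ART.** These answer the aim, but they use the before value inefficiently. With no multiplicity rule, the chance of a false antimicrobial claim exceeds 5%.
- **Unpaired tests of before against after within an arm.** These ignore the pairing. The t-test could be meant as paired, but the only non-parametric test named is for independent samples.

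Contrast, test and scale decide the antimicrobial conclusion, and all three could be settled after the data are seen. The statistician is blinded to group, which limits steering towards an arm, but blinding neither controls the error rate nor restores lost power.

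**Working it through.** **The plan's own figure.** No sample size or power is given for microbiology. The 30 per group for clinical success (95% vs 67%) reproduces with a two-sided, pooled formula without continuity correction: (1.96·√(2·0.81·0.19) + 0.8416·√(0.95·0.05 + 0.67·0.33))² / 0.28² = 29.6, so 30. Losses of one sixth give 30/(1 − 1/6) = 36. This fixes only the number of pairs per arm, taken here as 36, with 30 as the lower case.

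**Assumptions.** Log counts bivariate normal; equal before and after SD (set to 1); before/after correlation ρ = 0.3, 0.5, 0.7; true difference 0.5 SD. None of these is in the documents.

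**1. Family-wise error, unadjusted 5% tests (simulation).**

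- Two gel-vs-ART contrasts: 9.0% per organism, the same at 30 and 36 per arm.
- The same over two organisms: 13.7% (between-organism correlation 0.8) to 17.3% (independent).
- All three pairs, one organism: about 12%.

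**2. Between-arm power, 36 per arm.** The variance per tooth is 2(1 − ρ) for change and 1 − ρ² for ANCOVA. Their ratio is (1 + ρ)/2 = 0.65/0.75/0.85. Power is approximately Φ(δ − c), where δ = 0.5/√(variance·2/36). Critical values c are 1.994 (two-sample t), 1.983 (ANCOVA), 2.242 (Dunnett, two contrasts) and 2.378 (Tukey, three pairs). Example at ρ = 0.5: change δ = 0.5/√(1.0·2/36) = 2.121, Φ(0.127) = 0.55; ANCOVA δ = 0.5/√(0.75·2/36) = 2.449, Φ(0.466) = 0.68 unadjusted and Φ(0.207) = 0.58 with Dunnett.

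| Analysis | ρ=0.3 | ρ=0.5 | ρ=0.7 |
|---|---|---|---|
| Change t-test, unadjusted (simulated) | 0.427 | 0.555 | 0.771 |
| Change Mann-Whitney, unadjusted (simulated) | 0.408 | 0.531 | 0.750 |
| ANCOVA, unadjusted (simulated) | 0.596 | 0.676 | 0.834 |
| ANCOVA, Dunnett, two contrasts (simulated) | 0.496 | 0.581 | 0.761 |
| ANCOVA, Tukey, three pairs (formula; δ = 2.224/2.449/2.970) | 0.44 | 0.53 | 0.72 |

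Simulated family-wise error for Dunnett-adjusted ANCOVA is 0.050/0.050/0.051. The cost of adjustment within ANCOVA is 0.596 − 0.496 = 0.100, 0.676 − 0.581 = 0.095 and 0.834 − 0.761 = 0.073. At 30 per arm the change t-test gives 0.369/0.480/0.690 and Dunnett ANCOVA 0.417/0.496/0.673.

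**3. Equal-SD assumption.** With after/before SD ratio k, the variance saved by ANCOVA over change is 1 − k²(1 − ρ²)/(1 + k² − 2ρk). For k = 1 this is 0.35/0.25/0.15; for k = 0.5, 0.76/0.75/0.77; for k = 2, 0.04/0.00/0.07. It is never negative, but it can vanish.

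**4. Pairing ignored within an arm, 36 pairs, 0.5 SD shift (simulation).** Mann-Whitney has true alpha 2.3%/0.7%/0.1% and power 0.536/0.538/0.557. The paired t-test has 0.695/0.829/0.965 and the signed-rank test 0.678/0.810/0.956. At a 1 SD shift every test exceeds 99%.

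**5. Zero after-counts (simulation, ρ = 0.5).** With 30%/50% zeros, Dunnett ANCOVA power is 0.419/0.301 and rank ANCOVA 0.480/0.384, both at about 5% family-wise error. On the log scale, placing zeros 0.05, 0.3, 1 or 2 SD below the smallest observed value (30% zeros, true difference 0.5 SD) gives an estimated effect of 0.31, 0.35, 0.48 or 0.68 SD. Ranks do not depend on that placement.

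**The case against.** The strongest reply is that no invalid test is planned. Two-sample tests on change fit the aim and are valid, and the within-arm reading is not the stated aim, is conservative, and makes no difference for a large shift. This stands: a reader might infer that the named tests are wrong for these data, and the text does not support that. The fault is that the contrast is unspecified, and that the valid reading is inefficient and unadjusted.

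Other stronger readings also fail:

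- **Two contradictory units.** Intervention weighs each sample, holds it in 1 mL of saline and plans CFU/mg, so CFU/ml is naturally the laboratory step before it. What is missing is a sentence making that link. Bias from omitting weights would arise only if the planned weights were unused, and its size rests on invented weight ratios.
- **An undefined organism.** The abstract speaks of streptococci in general, but the agar is listed as selective for S. mutans and the culture step runs "for 72 hours to detect Streptococcus mutans count". The abstract wording is loose.
- **Inflation from several teeth per child.** All lesions indicated for treatment are sampled, so it is possible. Arms are counted in children, however, and no share of children with two teeth or intraclass correlation is given. A rule is needed, but no inflation figure can be claimed.
- **Free error control.** Setting adjusted ANCOVA beside unadjusted change scores hides the 7 to 10 points that adjustment itself costs.

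It can also be argued that adjusting a secondary outcome is a matter of preference. That is fair across organisms. Within an organism, two contrasts sharing one control are the stated aim, and the rule should be written down.

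**Conclusion.** The point holds as a should-fix on a secondary outcome. The plan leaves contrast, test and scale open for paired counts in three arms. The valid reading carries about 9% family-wise error per organism for two contrasts.

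Under equal SDs, a 0.5 SD difference and correlation 0.3 to 0.7, Dunnett-adjusted ANCOVA brings that to 5% with power between 7 points above and 1 point below unadjusted change scores. The ANCOVA gain roughly pays for the adjustment. With all three pairs adjusted the cost against unadjusted ANCOVA rises to about 11 to 15 points, and power ends 1 point above to 5 points below unadjusted change scores. If the after SD were twice the before SD, the ANCOVA gain would largely disappear and the adjustment cost would not be offset.

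The error rates do not depend on the assumed before/after correlation; the power figures do. Nothing here touches the primary comparison or the sample size.

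**What to change.** Replace the clause in Statistical Analysis with the following, for each organism:

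1. Outcome: log10 CFU/mg, with the CFU/ml of the enumeration step stated as the intermediate laboratory value.
2. Main analysis: ANCOVA across the three arms, after value on before value. Report Dunnett- or Holm-adjusted p-values for each gel against ART. If Brix 3000 against Papacarie duo is also tested, as the rationale at the end of the Introduction implies, adjust over all three pairs (Tukey or Holm).
3. Any within-arm change: paired t-test or Wilcoxon signed-rank test.
4. Unit of analysis: one pre-specified tooth per child, or child as a random effect.
5. Zeros: if zero after-counts are common, use rank-based ANCOVA rather than an arbitrary substituted value. The documents give no basis for a numerical threshold, so the team should either write its own criterion before group codes are released or adopt the rank-based analysis from the start.

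The cost is a short paragraph of text and slightly more analysis work. Weights and paired counts are already planned, so no new data or patients are needed. The statistical price is the loss of power from adjustment given above.
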